#### 3. Abstract.

Modulation of a patient's diet, specifically via short-term dietary protein restriction, can impact changes in cell energetics and dampen the normal subclinical inflammatory state. These changes can provide benchmarks for future research focused on using nutritional interventions aimed at improving the probability of a successful outcome following open aortic aneurysm surgery. We will conduct a short term dietary restriction study to characterize these changes in a normal control cohort. Knowledge gained from these experiments will be used in comparison to patients undergoing major surgery during a future study, as well as to identify the optimal time points for sample collection in our surgical population. These changes will be characterized by looking at inflammatory cells in the blood, proteins excreted in the urine, changes in microbiome signature of the stool and oral mucosal bacteria, as well as changes in skeletal muscle energetics derived from small biopsies.

## 4. Background

Our group is interested in developing a robust prospective translational research effort that focuses on patients undergoing open abdominal aortic aneurysm (AAA) repair since they have some of the highest rates of postoperative morbidity and mortality compared to other elective non-cardiac surgical patients. The underlying biologic basis of frailty in AAA patients that makes some subjects more vulnerable to postoperative complications is poorly understood. Short-term dietary protein restriction (stDPR) is a cost-effective, easily applied intervention that has strong pre-clinical data supporting efficacy in reducing surgical stress responses. Moreover, recent data supports the feasibility and safety of using stDPR to reduce adverse outcomes after cardiac surgery. These seminal observations offer a unique opportunity for application to other high-risk surgical patient populations known to have significant post-operative adverse event rates. Before initiating a clinical trial in AAA subjects, we need to characterize observations in healthy control, non-surgical subjects who are exposed to stDPR. Therefore, this pilot study is

designed to explore the ability of stDPR to impact the sub-clinical inflammatory milieu and skeletal muscle bioenergetics in a cohort of healthy, non-surgical patients.

**5. Aim**: Examine the baseline and early changes in muscle energetics, microbiome, and cell-mediated inflammation in healthy control patients receiving short-term dietary protein restriction.

#### 6. Research Plan

Overview: Using targeted assays of mitochondrial energetics, 10X genomics, and the microbiome, we will assess changes in skeletal muscle bioenergetics and the leukocyte transcriptome induced by a prescribed 96-hour protein restriction diet, tracking the impact of these changes on the dynamic response patterns of these parameters in healthy control patients.

Study Time points Summary							
	Days -7 to -1	Baseline/Day 0	Day 2	Day 4	Day 7	Day 14	
Consent	x						
Paffenbarger IQ	х						
IPR Study IQ		х	х	х	х	х	
Stool Kit Distribution	x	х	х				
Diet Kit Distribution		х	х				
Blood		х	х	х	х	х	
Urine		х	х	х	х	х	
Feces		х		х	х		
Cheek Swab		х	х	х	х	Х	
Muscle Biopsy		х		х	х		
Meal Logger				Days 5 thru 14			

Health Questionnaires: We will collect height and weight information to be utilized in the diet equation, as well as 2 questionnaires. The first is a physical activity Paffenbarger questionnaire which is used for the diet equation (see below) and an IPR study questionnaire to track energy level, mental awareness, and digestive issues.

Diet Modification: Subjects will follow a 4 day protein restricted diet using Scandishake® mixed with almond milk which will be provided. They may also drink water. No food, other beverages, or alcohol may be consumed. The amount of diet to be consumed will be calculated for each patient based upon resting energy expenditures plus additional energy needs using the Paffenberger IQ. REE = 9.99 x weight (KG) + 6.25 x height (cm) - 4.92 x age + 166 x sex (males, 1; females, 0) - 161. Patients will receive the study diet (ScandiShake® [any of 4 flavors] mixed

with almond milk), calculated individually for a total daily volume to achieve 30% caloric restriction and 70% protein restriction. These will be consumed by the study subjects at home in an unrestricted manner, in that they may be consumed at any point of time in the day.

Blood Collection and Cell Isolation and 10X Barcoding and RNA Sequencing. A 20 ml blood sample will be obtained via venipuncture before (Day 0), during (Day 2) and after completion of the 4 day protein restricted diet (Days 4, 7 and 14) for a total of 5 samples. These will be collected by [name] in the vascular clinic or vascular lab at the VA. Peripheral blood monocytes and neutrophils are isolated using a modified Ficoll method which can isolate both cell types. These samples are then subjected to bar coding with 10X reagents, followed by library preparation and RNA sequencing at approximately 30 million reads per sample (2 x 150 PE). Analysis of data will be primarily performed using 10X proprietary software, Cell Ranger, which is a set of analysis pipelines that process Chromium single-cell RNA-seq output to align reads, generate feature-barcode matrices and perform clustering and gene expression analysis. Cell Ranger includes four pipelines relevant to single-cell gene expression experiments.

Skeletal Muscle Mitochondrial Phenotypina: Collection of 3 tissue samples from the thigh; before and after the protein restrictive diet on Day 0, Day 4 and Day 7 will occur. We will utilize a minimally invasive microbiopsy technique (skin puncture) to obtain skeletal muscle biopsies of the vastus lateralis muscle. These will be collected by [name] in the vascular clinic at the VA. Multiple aspects of mitochondrial function (basal and ADP-stimulated respiratory kinetics under multiple substrate combinations, H2O2 production and emitting potential, mitochondrial Ca2+ retention capacity) will be assessed in duplicate on permeabilized fiber bundles from freshly obtained muscle biopsy samples. The permeabilized fiber approach permits in situ study of mitochondrial function in real-time, retains the native reticular network structure of mitochondria in muscle, and requires very little tissue per protocol (~1.5 mg wet weight). All mitochondrial functional analyses are completed in real time within 2-3 h. Fibers are then freeze dried overnight, weighed, rehydrated, and freeze fractured for determination of citrate synthase activity. All data are expressed per dry weight and/or mitochondrial content.

Microbiome Sample Processing: Three stool samples will be collected on Day 0, Day 4, and Day 7. Stool collection kits and instructions will be given to patients at their screening visit. Patients will collect their feces in a toilet insert (similar to an upside down hat) and will take a walnut sized scoop of this feces using a provided tube/scooper and insert it in the collection container and bag. Stool samples may be collected at home within 24 hours of the clinic visit or during clinic visits on Day 0, 4 and 7. In addition, a swab of cheek saliva will be collected using a sterile swab and placed into a provided sterile tube. DNA will be extracted from these samples using DNeasy PowerLyzer PowerSoil Kit (Qiagen) and will be quantified using spectrophotometry. Amplification of 16S rRNA will be performed to create amplicons, after which PCR will be used to add adapters and dual-index barcodes to the amplicon target. These libraries will be pooled together for sequencing by Illumina MiSeq. Reads will be assigned to operational taxonomic units, which will enable us to identify phyla, classes, families, and genera in each sample. The MiSeq run output is approximately >20 million reads and can generate sufficient reads for metagenomic surveys.

Operational taxonomic units (OTUs) for bacterial species at each time point will be determined for all patients. Both alpha-diversity (overall diversity) and beta-diversity (composition of species) measurements will be obtained from these OTUs. Mann-Whitney tests will be used to compare alpha diversity in patients who developed post-operative complications to those who did not. One-way analysis of variation (ANOVA) or Kruskal-Wallis tests will similarly be conducted to compare beta-diversity  $^{21}$ . Heatmaps with clustering for relative abundance of species at the genus level will be created for all samples and pairwise differences between preoperative and post-operative samples will be identified. The response will be measured as a change from baseline, and the baseline response will be included as a covariate in the subsequent multivariate analysis. In addition to this, we will perform principal component analysis (PCA) to create a mixed multivariate model with the intent of combining laboratory values for IL-10, LXA4, TNF- $\alpha$ , and annexin-1 with OTUs.

Urine sample processing for ketones: Collection of 5 urine samples will occur on Day 0, 2, 4, 7 and 14. Urine will be collected in a cup and approximately 1 ml of urine will be stored for later analysis. While on diet and immediately following completion of the diet, ketones are a marker for diet compliance, as well as urinalysis will attempt to understand the physiologic impact of the diet on renal function can occur through processing for serum ketones (that get generated on diet). Commercially available assays can quickly evaluate these parameters which will further assist in determining the time-dependent, physiologic effects of this nutritional intervention in healthy control subjects.

De-identified biologic samples will be stored in refrigerator/freezers within the PI's designated research space for the duration of the study. Unused samples will be discarded in the appropriate safety disposal container.

Mealogger App – This is a free app available on smartphones in which patients take a picture of the meals they ingest to approximate their normal food intake following the study. This will begin day 5 and will complete on day 14 of the study. During clinic visits, the patients will open the app so that study coordinators can record information about what foods consumed and the caloric/protein content patients exposed themselves too after completion of the study diet. This information will be recorded with the other study data in a de-identified manor.

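### Hour of sampling and time since last intake are neither fixed nor recorded, so they cannot be separated from the diet effect in blood and urine, and possibly in muscle

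*Protocol*

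**What the plan says.** All the relevant text is in section 6 (Research Plan) of the protocol.

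- **Diet Modification.** The shakes are "consumed by the study subjects at home in an unrestricted manner, in that they may be consumed at any point of time in the day". The overview attributes the changes of interest to the diet, as "induced by a prescribed 96-hour protein restriction diet".
- **Blood.** Samples are "obtained via venipuncture before (Day 0), during (Day 2) and after completion of the 4 day protein restricted diet (Days 4, 7 and 14").
- **Muscle.** Three biopsies: "before and after the protein restrictive diet on Day 0, Day 4 and Day 7 will occur". There is none on Day 14.
- **Urine.** "Collection of 5 urine samples will occur on Day 0, 2, 4, 7 and 14". While subjects are on the diet and just after it, "ketones are a marker for diet compliance".
- **Meal app.** From Day 5 to Day 14 subjects "take a picture of the meals they ingest to approximate their normal food intake following the study". Coordinators record the foods and their calorie and protein content. Meal times are not mentioned.

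The only sampling window is for stool, which may be collected at home within 24 hours of the visit. The Compensation table gives the length of each visit, not its hour.

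**The concern.** The study estimates change within subjects. The participants are called healthy controls, but all of them take the diet and no undieted group is described. Each kind of specimen has one pre-diet sample and one sample per later visit. Whatever else differs between two visits therefore enters the change score together with the diet.

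Hour of day and time since last intake can differ freely. Under the protocol as written, a subject might be sampled in the morning after an ordinary meal on Day 0, in the afternoon soon after a shake on Day 2, and after a long gap on Day 4. If these conditions affect the measurements within hours, the change over days absorbs that effect. Because neither time is recorded, no later analysis can remove it.

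The stated purposes depend on this. The Abstract wants benchmarks for a later surgical study and a choice of its sampling times. The urine subsection looks for time-dependent physiological effects.

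**Working it through.** **1. What is fixed for each specimen**

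| Specimen | Days | Clock hour | Intake state before sampling | Times recorded |
|---|---|---|---|---|
| Blood | 0, 2, 4, 7, 14 | not set | not set | not mentioned |
| Urine | 0, 2, 4, 7, 14 | not set | not set | not mentioned |
| Muscle | 0, 4, 7 | not set | not set | not mentioned |

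The meal app does not cover Days 0 to 4, which include the baseline and the diet itself. The study questionnaire is described as tracking energy, mental awareness and digestion, not intake times.

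**2. Where the shake rule applies.** It bears directly on Day 2 and, depending on when the last shake is taken, on Day 4. On Days 0, 7 and 14 subjects are not on shakes; the gap there is that hour and intake state are unset.

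**3. What goes into a change score.** Write the measurement at visit k as subject level + D(k) + T(k) + e(k). D is the diet effect, with D(0) = 0; T is the effect of hour and recent intake; e is all other within-subject variation. Then

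change(k) = D(k) + [T(k) − T(0)] + [e(k) − e(0)].

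With one arm and one baseline, D(k) and T(k) − T(0) cannot be estimated separately unless T is held constant or its causes are recorded.

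**4. Random differences.** The protocol gives no SD, so the size of T is assumed. Let SD(e) = s and SD(T) = r·s, independent between visits. Then

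SD(change) = √(2s² + 2r²s²) = s√2 · √(1 + r²),

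so the SD, and with it the confidence interval width at a given n, is multiplied by √(1 + r²):

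- r = 0.5: √1.25 = 1.118, which is 12% wider
- r = 1.0: √2 = 1.414, which is 41% wider

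For scale, take the planned 10 subjects and suppose a two-sided paired t-test at 5%. Without T, 80% power needs a true change of 1.00 SD of the change. With r = 0.5 or 1.0 that becomes 1.11 or 1.41 SD, and power at 1.00 SD falls to 71% or 51%. The test is an illustration; the protocol names none for these outcomes.

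The inflation would be smaller if subjects happened to attend under similar conditions each time, because T would partly cancel, or if true responses to the diet vary between subjects, because that variation enlarges the base.

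**5. Systematic differences.** If T(k) − T(0) averages b over subjects, the mean change estimates D(k) + b, and a larger sample does not remove b. Nothing in the document gives b.

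**6. Ketones.** If the reading also moves with time since last intake, a compliant subject sampled soon after a shake and a non-compliant subject sampled after a long gap may look alike. This affects about Days 2 and 4, where the protocol uses ketones for compliance.

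**The case against.** The shake sentence governs intake at home, not sampling, and states nothing wrong in itself. For Days 0, 7 and 14 the complaint is an omission, and a visit schedule or laboratory manual might fill it. This stands in part. No such manual is mentioned, however, and sampling conditions cannot be left to a later analysis plan, because unrecorded times are lost.

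The muscle argument is weaker than the one for blood and urine. Respiration is measured in permeabilized fibers under substrate combinations set by the assay, and results are expressed per dry weight or mitochondrial content. The last meal does not supply those substrates. Some acute effect may remain, but the document does not show one, so muscle is only possibly affected.

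That these measurements respond within hours to feeding or time of day is a premise, not something the protocol states. The protocol also does not give the composition of the shake beyond product, almond milk and restriction targets. The omission is certain; its consequence is plausible but unsized.

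A reader might go further and infer a high rate of false diet effects. A systematic shift of 0.3, 0.5 or 0.8 SD of the change would make a two-sided paired t-test in 10 subjects reject 14%, 29% or 62% of the time with no true effect, instead of 5%. The documents do not support that as a finding. It needs a shift in the same direction across subjects, for which they give no evidence, and a test they do not specify. Subjects varying in different directions add noise, not bias. A reader might also extend the muscle concern to Day 14 or the ketone concern to all five visits; the sampling schedule rules out the first, and the limited period of the compliance use rules out the second.

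**Conclusion.** The point holds in a limited form. Intake time on the diet is expressly free, and no visit has a set hour or pre-sample intake state, or a record of either. In a single-arm before-after design with one baseline sample, these factors cannot be separated from the diet effect in blood and urine across the five visits, and possibly in muscle across Days 0, 4 and 7. Compliance readings from ketones at about Days 2 and 4 are weakened.

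The expected cost is noise: 12% to 41% on the SD and confidence interval width of a change, if timing adds 0.5 to 1.0 times the other within-subject SD independently at each visit. Bias would arise only from a systematic difference between visits. Both the assumed range and the possibility of bias come from outside the document, which allows no estimate of either. The sponsor should act on this before enrolment, because the times cannot be recovered afterwards.

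**What to change.** In the diet, blood, muscle and urine subsections of section 6:

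1. Schedule each subject's later visits in the same clock window as that subject's Day 0 visit.
2. Sample in the same pre-sample intake state at every visit. The sponsor should choose that state and reconcile it with the sentence that leaves intake time unrestricted, since a rule for Days 2 and 4 touches when shakes can be taken on those days.
3. Record the sampling time and the time of last intake at each visit.
4. State that these times are used when interpreting ketones and the changes from Day 0.

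Diet content and amount stay as they are. The cost is protocol wording, two data fields per visit and less flexible appointments for 10 subjects; no visit, sample or staff is added. If the sponsor cannot standardise the visits, recording the two times is the minimum worth doing.

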# Subject Enrollment

We anticipate enrolling 10 patients for up to a year following study initiation. Patients who express interest in learning more about the study will meet with a member of the study staff who will describe the study, review the informed consent form, give them a copy of the informed consent to read and answer any questions. Potential participants will be allowed to take a copy of the consent form, as well as written information about the study if they so desire. When possible, signing of the consent shall occur at least one day prior to diet initiation to allow adequate time for patient to make consideration without any stress. Any questions will be answered by the Principal Investigator or other study team members.

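### Does naming Cell Ranger as the main tool for the single-cell RNA data mean that cells, and not the 10 subjects, become the replicates for the diet effect?

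*Protocol*

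**What the plan says.** The overview in Protocol section 6 (Research Plan) makes the transcriptome an objective: "we will assess changes in skeletal muscle bioenergetics and the leukocyte transcriptome induced by a prescribed 96-hour protein restriction diet". The blood-collection paragraph of the same section schedules draws on Days 0, 2, 4, 7 and 14, five per subject. Subject Enrollment sets the size: "We anticipate enrolling 10 patients". That makes 10 independent units and up to 50 samples.

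On analysis, the blood-collection paragraph says: "Analysis of data will be primarily performed using 10X proprietary software, Cell Ranger". It then describes the software as pipelines that "process Chromium single-cell RNA-seq output to align reads, generate feature-barcode matrices and perform clustering and gene expression analysis". It gives a sequencing depth of about 30 million reads per sample but no number of cells. It does not say how the five days will be compared.

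Two other places bear on the point. The Statistical Analysis statement, printed after the compensation table, gives that work to a departmental statistical support group, blinded to patient identifiers, and states no method. Section 4 (Background) calls the study a pilot "designed to explore the ability of stDPR to impact the sub-clinical inflammatory milieu and skeletal muscle bioenergetics". The protocol sets no significance level, hypothesis test or decision rule for the transcriptome.

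**The concern.** The only analysis named for the transcriptome is a single-cell pipeline, it is called the main one, and its description includes gene expression analysis as well as alignment and counting. The question, however, is about change within subjects over time. Cells from one draw share that draw's biology and processing. If Day 4 cells were tested against Day 0 cells as if each were independent, the shared variation would be counted many times over as evidence.

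The stake would be real. Section 3 (Abstract) expects the observed changes to serve as benchmarks for later work, to be compared with surgical patients, and to guide the choice of sampling times. Spurious diet effects could pass into that next study.

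**Working it through.** The protocol states no power, error rate or effect size for the transcriptome, so there is no figure of its own to reproduce. Two things can be checked: how large the inflation would be if cells were the replicates, and whether the protocol says they will be.

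**1. Size of the effect, if cells were the replicates**

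Inputs from the protocol: 10 subjects (Subject Enrollment) and one sample per subject per visit (section 6). Inputs that are assumptions, because the protocol gives neither: *m*, the cells per sample, and ρ, the share of per-cell variance that lies between samples of the same subject.

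Design effect: D = 1 + (m − 1)ρ. True type I error of a nominal two-sided 5% cell-level test of one visit against Day 0: 2 × [1 − Φ(1.96/√D)].

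Worked case, m = 500 and ρ = 0.02: D = 1 + 499 × 0.02 = 10.98; √D = 3.31; 1.96/3.31 = 0.59; type I error ≈ 55%.

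Over a range of assumptions:

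| m | ρ = 0 | ρ = 0.001 | ρ = 0.01 | ρ = 0.05 |
|---|---|---|---|---|
| 100 | 5% | 6.2% | 16.5% | 42% |
| 500 | 5% | 10.9% | 42% | 70% |
| 1000 | 5% | 16.6% | 55% | 78% |
| 3000 | 5% | 32.7% | 72.5% | 87% |

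A simulation of 20,000 runs agrees. At m = 1000 and ρ = 0.01 the cell-level test rejected in 55.8% of runs, and a paired t test on 10 subject-level means (9 degrees of freedom) in 5.0%. For m from 500 to 3000 and ρ from 0.005 to 0.05, the paired test stayed between 4.8% and 5.2%.

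The arithmetic is sound. Its result runs from no inflation to 87%, depending wholly on two quantities that the document does not contain.

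**2. Does the protocol prescribe that test?**

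- *Unit of analysis.* Nothing in section 6 makes the cell the unit for the diet comparison.
- *Where visits are compared.* The software is said to align, build matrices, cluster and analyse gene expression. The text does not say that Day 0 is set against later days within it. Expression analysis of single-cell output can mean describing clusters within a sample just as well as contrasting visits.
- *How the software tests.* The statement that its comparison has no subject term and no pairing describes the inside of a proprietary program. The protocol does not contain it, so it cannot be established from the document.
- *Whether anything follows.* The word "primarily" in "Analysis of data will be primarily performed using 10X proprietary software, Cell Ranger" leaves room for further analysis, and the Statistical Analysis statement assigns statistical work to a separate group.

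**3. Does it follow that false positives would dominate the results?**

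No. The calculations cover null genes only. The share of false calls among all calls also depends on how many genes truly change and on the power to detect them, and neither is known. The protocol also mentions no gene list to be carried forward.

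**The case for a change.** The strongest case for the concern is that the protocol did not stay silent on the method. It picked a tool, called it the main one, and included expression analysis in its description. For the microbiome, section 6 does state change from baseline with the baseline as covariate, so the authors could have written the same for the transcriptome and did not. The Statistical Analysis statement says who does the work and that it is blinded, but not how. Exploratory status is no full protection either, since the results are meant to inform a later study.

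Much of this stands. The quotation is exact, no other transcriptome analysis is named, the change-from-baseline sentence does belong to the microbiome paragraph, and cell-level testing of visits would inflate type I error over most of the assumed range. But these facts show only that the subject-level model is not written down. They do not show that a wrong one is. Using Cell Ranger for alignment, counting and clustering is no error, and an analysis that sums counts per subject, day and cell type would start from its output. Blocking on subject, summing counts and controlling the false discovery rate are details that a protocol commonly leaves to the statistical analysis plan.

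**Conclusion.** The concern does not hold. The protocol names software for processing and exploring single-cell data. It does not state a rule under which cells replace subjects in the comparison of visits. The inflation is a correct calculation about an analysis that the document does not prescribe: about 55% at m = 500 and ρ = 0.02, and anywhere from 5% to 87% over the range in the table. It rests on an assumed number of cells, an assumed correlation and an assumed test.

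This conclusion takes the text as it stands. No statistical analysis plan was available, though one may exist. A plan that did test one day's cells against another's as independent observations would have the problem in full, and the calculation above would then apply with that plan's own cell numbers.

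### Two microbiome comparisons are defined by surgery, but the cohort is about 10 healthy volunteers who have no operation

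*Protocol*

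**What the plan says.** Section 5 (Aim) of the protocol sets the purpose: "Examine the baseline and early changes in muscle energetics, microbiome, and cell-mediated inflammation in healthy control patients" on the diet. The microbiome is one of the three domains named there.

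The Microbiome Sample Processing paragraphs of section 6 give the plan for that domain:

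- Sampling: "Three stool samples will be collected on Day 0, Day 4, and Day 7". A cheek swab is also taken; the schedule at the start of section 6 places it on Days 0, 2, 4, 7 and 14.
- Profiles: "Operational taxonomic units (OTUs) for bacterial species at each time point will be determined for all patients".
- Alpha diversity: "Mann-Whitney tests will be used to compare alpha diversity in patients who developed post-operative complications to those who did not".
- Beta diversity: "One-way analysis of variation (ANOVA) or Kruskal-Wallis tests will similarly be conducted to compare beta-diversity". No grouping factor is named.
- Genus-level abundance: heatmaps for all samples, after which "pairwise differences between preoperative and post-operative samples will be identified".
- Response: "The response will be measured as a change from baseline", with the baseline value as a covariate in the multivariate analysis, followed by a model built on principal components.

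The population is described elsewhere. Section 4 (Background) describes a healthy, non-surgical cohort, Subject Selection admits healthy volunteers aged 18 to 70, and Subject Enrollment anticipates 10 of them. Section 3 (Abstract) leaves patients having major surgery to a later study.

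**The concern.** Two of the stated comparisons take their groups or time points from an operation that nobody in this study has. The alpha-diversity test needs people who had surgery and then did or did not have a complication. The pairwise contrast needs samples from before and after an operation. Both read as text written for the planned aneurysm-surgery study.

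At stake is whether the protocol's named tests answer its own Aim, which asks about change over the diet days. The alpha-diversity sentence is the only place where the microbiome plan gives both a test and its two groups, and that test yields nothing here. If the text stands, the analyst will have to choose replacement contrasts, possibly after seeing the data, from two post-baseline stool days and four post-baseline swab days.

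**Working it through.** The protocol gives no significance level, power, effect size or standard deviation for the microbiome, so there is no planned figure to reproduce. The check is whether the stated comparisons can be formed from the planned cohort.

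**Inputs**

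- Participants: 10 (Subject Enrollment), in a single cohort.
- Operations: none (section 4; schedule in section 6).
- Stool days: 0, 4, 7 (section 6).
- Swab days: 0, 2, 4, 7, 14 (schedule in section 6).

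**Complication comparison.** With no operation, the number with a post-operative complication is n1 = 0. Counting everyone else as free of complications gives n2 = 10. This is generous: strictly, the second group should also have had surgery, and then it is empty too.

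- Mean of the Mann-Whitney statistic: n1·n2/2 = 0 × 10/2 = 0.
- Variance: n1·n2·(n1 + n2 + 1)/12 = 0 × 10 × 11/12 = 0.
- The standardised statistic is therefore 0/0, which is undefined.
- Possible allocations for an exact test: C(10, 0) = 1, so there is nothing to compare the observed allocation with.

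Run in standard software with groups of 0 and 10, the test returns no statistic and no p-value.

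**Preoperative against post-operative samples.** Assuming all samples are obtained:

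- Stool: 10 × 3 = 30.
- Swabs: 10 × 5 = 50.
- Total: 30 + 50 = 80, of which 0 are preoperative and 0 post-operative.

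If the label means before and after the diet, pairs exist but the label does not pick them out. Stool has one day before (Day 0) and two after (Days 4 and 7). Swabs have one before (Day 0), three after (Days 4, 7 and 14), and Day 2. The blood collection paragraph, which uses the same five days, places Day 2 during the diet.

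**What the design can support.** Within-subject contrasts against Day 0 have up to 10 pairs each: two for stool (Days 4 and 7) and four for swabs (Days 2, 4, 7 and 14). With 10 pairs the smallest two-sided exact signed-rank p-value is 2/2^10 = 2/1024 = 0.00195, so such a test can be run and can give a small p-value.

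**The case against.** The best defence is that the rest of the plan fits the design. Profiles by time point, heatmaps of all samples, a change-from-baseline response with baseline as covariate and the component-based model need no surgery. Together they give a within-subject framework anchored to Day 0. The preoperative and post-operative wording can be taken as a carried-over label for before and after the diet, and the choice of days to pair could be left to a statistical analysis plan. The protocol states no primary endpoint, hypothesis or power claim for the microbiome.

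Most of this stands, and it limits the point. It does not rescue the complication sentence. No diet day can stand in for a post-operative complication, and the protocol defines no other event for that role. An analysis plan could only contradict the sentence.

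A reader might infer three stronger things that the document does not support.

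- **That the whole microbiome plan fails.** It does not, given the unaffected analyses just listed. Nor is the alpha-diversity test fully specified apart from its groups: no index, sample type or day is named.
- **That the beta-diversity test is also wrong.** Its sentence names no factor. If its link to the preceding sentence carries over the complication split, it repeats the same fault. If not, the missing factor is a detail that an analysis plan may supply.
- **That a one-way test by day would produce false positives.** The document gives neither a by-day grouping nor a within-person correlation. In an illustrative simulation of 10 people on three days, with one score per sample and correlations assumed from 0 to 0.7, Kruskal-Wallis rejected a true null in 4.8% down to 0.1% of runs at a nominal 5%. That is lost sensitivity, not excess error, and the point does not rest on it.

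**Conclusion.** The point holds as a contradiction within the current protocol text. The alpha-diversity comparison by post-operative complications cannot be run in this cohort on any reading. The pairwise contrast cannot be run as labelled, and on a charitable reading it still needs its days named.

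The severity is moderate: it should be fixed, but it does not threaten the study. It concerns two stated comparisons in one of three domains of an exploratory pilot. Sampling, participants and the other microbiome analyses are untouched. The conclusion rests only on the cohort being non-surgical, which the protocol states. The group and sample counts assume the anticipated 10 participants with complete sampling; another enrolment figure would change the counts but would still leave the complication group empty.

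**What to change.** In section 6, Microbiome Sample Processing:

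1. Delete the comparison by post-operative complications, or state that it belongs to the future surgical study.
2. State that alpha diversity is compared within subject against Day 0, for stool on Days 4 and 7 and for swabs on Days 2, 4, 7 and 14, by a paired or repeated-measures method.
3. Replace the preoperative and post-operative labels with the diet days to be compared.
4. As a secondary point, if beta diversity is meant to be compared across days, use a method that respects repeated samples from the same person in place of one-way ANOVA or Kruskal-Wallis.

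The diversity index, the exact method and other detail can be left to the statistical analysis plan. The cost is protocol wording only, with no extra samples, visits or participants. The change should be made before the microbiome data are analysed, so that the contrasts are not chosen with results in view.
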